Figure 2. Saphenous vein graft (SVG) and internal mammary artery (IMA) patency rates after CABG in VA Cooperative Studies #207/297/364.

SVG failure is critically important.

Mechanisms leading to saphenous vein graft failure

SVG failure is the result of 3 consecutive and inter-related processes: thrombosis, intimal hyperplasia, and atherosclerosis (Figure 3).^{11, 12} Immediately post CABG thrombus forms in SVGs due to endothelial disruption during harvesting and implantation. If the SVGs remain patent during this period, they develop a platelet-mediated progressive thickening of the vessel wall, which involves smooth muscle cell proliferation and extracellular matrix protein synthesis. Atherosclerosis subsequently develops on the ground of intimal hyperplasia, leading to decreased antegrade flow or eventually SVG occlusion.

[figure not shown]

Figure 3. Evolution of saphenous vein graft lesion development. After coronary artery bypass SVGs either occlude early or develop intimal thickening (panel 1), which forms the ground for moderate lesion development (panel 2). Moderate SVG lesions have high rates of progression to severe, symptom-causing lesions (panel 3), and eventually occlusion (panel 4).

SVG harvesting during CABG can cause significant injury, both at the time of removal from the leg and during SVG flushing to prepare the conduit for grafting.¹³ SVG wall injury may predispose to intraluminal platelet thrombus formation, which was observed in 68% of SVGs examined by OCT immediately post harvesting (Figure 4).¹³ Several factors may affect the severity of SVG injury, such as the mode of harvesting (endoscopic vs. open), manual high-pressure intraluminal distension, and the presence of baseline SVG disease. Lack

[figure not shown]

Figure 4. Identification of intraluminal thrombus formation in SVGs immediately after harvesting using optical coherence tomography (panel A) or by direct visualization (panel B).

of heparinization during SVG harvesting was associated with a trend for higher SVG occlusion rates one week post CABG, highlighting the risk for early SVG thrombosis.¹⁴

Several other factors are associated with decreased SVG patency, such as multiple distal SVG anastomoses¹⁵ and off-pump surgery,⁵ that is why SVGs with multiple anastomosis will be excluded from the present study; nearly all coronary bypass graft surgeries are performed on-pump at our institution.

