Gao et al ³⁰	clopidogrel	197	1 and 12 months	SVG patency, as assessed by computed tomography	Similar SVG patency in both study groups.
Gao et al ³¹	clopidogrel	249	3 months	SVG patency, as assessed by computed tomography	Higher SVG patency in clopidogrel group: 91.6% vs. 85.7%, p=0.043

CASCADE ¹²	clopidogrel	113	12 months	SVG intimal area at follow-up IVUS	4.5±2.1 mm ² in placebo vs. 4.1±2.0 mm ² in clopidogrel, p=0.44
PAPA CABG ³³	clopidogrel	100	30 days	SVG occlusion, as assessed by computed tomography	23.1% in placebo vs. 17.5% in clopidogrel groups had ≥1 occluded graft (p=0.54). Radial graft occlusion was lower in the clopidogrel arm (43.8% vs. 10.5%, p=0.05).

In addition to the above studies an analysis of the Clopidogrel in Unstable angina to prevent Recurrent ischemic Events (CURE) trial, showed that patients who underwent CABG had a trend for lower incidence of the primary endpoint (composite of cardiovascular death, myocardial infarction, or stroke) at 12 months [14.5% for clopidogrel 16.2% for placebo; relative risk (RR), 0.89; 95% CI, 0.71 to 1.11].³²

In summary 2 of the 5 published trials demonstrated benefit with thienopyridine on bypass graft patency and 3 did not. There are multiple possible explanations for these conflicting results. One explanation is that SVG thrombus is not important for maintaining early SVG patency, however this would contradict studies showing association of baseline SVG thrombus with subsequent SVG failure.¹⁴ A second possible explanation is that clopidogrel does not provide adequate platelet inhibition to successfully prevent SVG thrombus formation. Several studies have demonstrated variable antiplatelet response to clopidogrel depending on genetic factors and concomitant medication administration.³⁴ A third possible explanation is that the surrogate endpoint used in the CASCADE trial (intimal hyperplasia) may not be the best surrogate endpoint, and surrogate endpoints that directly assess SVG thrombus (such as OCT) may be more accurate.

7. Definition of the Population to Which the Study is Directed, with Justification:

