Approximately 120 patients will be randomized into this study at the Dallas VA Medical Center.

10. JUSTIFICATION FOR THE USE OF SPECIAL SUBJECT POPULATIONS:

Not applicable.

11. STUDY DESIGN:

The primary efficacy objective is to compare the prevalence of SVG thrombus as detected by optical coherence tomography of a target SVG between patients receiving prasugrel vs. placebo. We hypothesize that prasugrel will be superior to placebo in reducing the prevalence of SVG thrombus at 12-month follow-up OCT imaging.

The primary safety endpoint is the incidence of severe bleeding as defined using the GUSTO study criteria.⁶⁷ We hypothesize that patients receiving prasugrel will have similar incidence of severe bleeding compared to patients receiving placebo during the 12-month study period.

The secondary endpoints will be: (1) incidence of angiographic SVG failure (defined as $\geq 75\%$ SVG diameter stenosis in at least one SVG); the total and normalized total SVG atheroma volume within at least 40 mm of the target SVG, as assessed by intravascular ultrasonography; the lipid core burden index of the target SVG, as assessed by near-infrared intracoronary spectroscopy; and (2) the incidence of major adverse cardiac events and moderate bleeding during the 12-month study period.

The proposed study is a phase 3, single-center, randomized, double-blind, controlled, parallel-group study of prasugrel vs. matching placebo in patients with recent CABG, starting at the time of hospital dismissal from CABG (Figure 13). All patients will be receiving aspirin, as per standard current practice.

[figure not shown]

Figure 13: Flowchart of the proposed study design.

CABG = coronary artery bypass graft surgery; OCT = optical coherence tomography; IVUS = intravascular ultrasound; NIRS = near-infrared spectroscopy; R = randomization; m = month; FU = follow-up.

12. DESCRIPTION OF PROCEDURES TO BE PERFORMED:

The study design will be explained to the patients and if they agree to participate they will be asked to sign an informed consent form and they will receive a copy of the consent form. They will subsequently be randomized to prasugrel or placebo, as described below.

Randomization and Treatment

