One SVG will be examined in each patient. The target intermediate SVG lesion will be selected by the interventional cardiologist performing the procedure as the longest and least-angulated SVG amenable to intravascular imaging. After intragraft administration of 200 µg of nitroglycerin, an OCT catheter (DragonFly, St Jude Medical, Minneapolis, Minnesota) will be advanced 40-50 mm distal to the SVG proximal anastomosis and will be pulled back proximal to the lesion using a motorized system at a speed of 20 mm/sec. The OCT images will be written on CD-R or DVD for subsequent off-line analysis. Subsequently, a 45-MHz, 3.2F, rotational IVUS catheter (Revolution, Volcano therapeutics, Rancho Cordova, California, USA) will be advanced into the target SVG and the transducer will be advanced as distal as possible within the SVG and will then be pulled back to the SVG aortic ostium using a motorized pull-back system at a speed of 0.5 mm/s. During pullback, gray-scale IVUS will be recorded at a rate of 30 frames per second. The gray-scale IVUS movie will be written on CD-R or DVD for subsequent off-line analysis. Similarly, a 3.2-F near-infrared spectroscopy catheter (Lipiscan IVUS, InfraReDx, Burlington, Massachusetts) will be advanced into the target SVG and positioned to the same location where the IVUS catheter was previously placed, if feasible. The catheter will then be pulled back to the aortic ostium using a motorized pull-back system at a speed of 0.5 cm/s. A chemogram of the artery will be obtained, as shown in Figures 10-12. The near-infrared spectroscopy data will also be recorded in CD-R or DVD for subsequent analysis.

Examination of the target SVG lesion with angiography, OCT, IVUS, and NIRS will be obtained at 12 months post CABG. If the patient undergoes clinically-indicated graft angiography before the 12-month planned angiography, then: (a) if ≥ 10 months have elapsed from enrollment in the study, then angiography, OCT, IVUS, and NIRS of a target SVG will be performed; or (b) if <10 months have elapsed from enrollment, then prasugrel will be continued and the patient will be asked to return for the planned 12-month angiography, OCT, IVUS and NIRS.

Follow-Up: Study procedures and follow-up assessments are summarized in the below table 2.

Table 2. Schedule of observations and laboratory assessments.

Test	Treatment period						Post-Treatment Follow-up Contact (30 days after 12 month visit – Phone FU)

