The prevalence of thrombus within the target SVG at 12-month OCT imaging (primary efficacy endpoint) will be analyzed using the Fisher's exact test. In view of the relatively small sample size of the trial, multivariable logistic regression analyses will be performed to adjust the findings for any potential differences in the baseline characteristics of the two study groups, which are known to influence the occurrence of SVG failure. Such characteristics are: patient age, prior myocardial infarction; total cholesterol and HDL-cholesterol levels; minimum graft diameter; mean arterial pressure; ejection fraction; male gender; and current smoking.⁶⁹ The significant characteristics will be incorporated in the calculation of an adjusted odds ratio representing the association between treatment and the prevalence of thrombus, along with 95% confidence intervals. Because off-pump and endoscopic SVG harvesting may be associated with higher rates of SVG failure, randomization will be stratified by (a) on vs. off pump and (b) endoscopic vs. open harvesting.

The time elapsed to the incidence of severe bleeding, defined using the GUSTO criteria⁶⁷ (primary safety endpoint) will evaluated using Kaplan-Meier survival curves and compared between the 2 study groups using the log-rank test.

Statistical Analysis of secondary endpoints:

The differences in angiographic SVG failure, in total and normalized total SVG atheroma volume and in lipid core burden index at 12-month SVG imaging will be compared between the 2 study groups using Fisher's exact test. A logistic regression model will be developed to evaluate the treatment effect on this outcome adjusting for patient age, prior myocardial infarction; total cholesterol and HDL-cholesterol levels; minimum graft diameter; mean arterial pressure; ejection fraction; male gender; and current smoking.⁶⁹

The incidence of major adverse cardiovascular events (composite of death, acute coronary syndrome, and coronary revascularization) at 12 months will be compared between the two study groups using the chi-square test. Kaplan-Meier survival curves and the log-rank test will be used to compare time-to-event of major adverse cardiac events in the two study groups.

All tests will be two-sided. The critical level for the primary and four secondary outcomes will be 0.05. No adjustments will be made for multiple secondary endpoints

14. PROVISIONS FOR MANAGING ADVERSE REACTIONS:

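### Fisher's exact test is assigned to three numeric secondary endpoints (total and normalized atheroma volume, lipid core burden index) with no cut-off, so their comparison cannot be run as written.

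*Combined protocol and SAP*

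**What the plan says.** Section 11 (Study Design) defines the imaging secondary endpoints. Angiographic graft failure is binary, at a threshold of 75% diameter stenosis. The others are "the total and normalized total SVG atheroma volume within at least 40 mm of the target SVG", measured by IVUS, and "the lipid core burden index of the target SVG, as assessed by near-infrared intracoronary spectroscopy". Neither the two volumes nor the index has a threshold or categories.

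Section 13 (Statistical Analysis of secondary endpoints) then groups graft failure, both atheroma volumes and the index in one sentence, which ends: "lipid core burden index at 12-month SVG imaging will be compared between the 2 study groups using Fisher's exact test". The next sentence reads "A logistic regression model will be developed to evaluate the treatment effect on this outcome", followed by a covariate list. The section closes with two-sided testing at 0.05 and "No adjustments will be made for multiple secondary endpoints".

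The other methods named in Section 13 are chi-square, Kaplan-Meier with log-rank, and logistic regression. All are for binary or time-to-event data.

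**The concern.** Fisher's exact test compares counts in categories. It suits graft failure. It cannot be applied to a volume or an index until someone divides the scale, and the plan does not say where. The plan does not prescribe dichotomising either; it names a test that does not match the data.

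The adjusted analysis does not settle the matter. The logistic model refers to a single outcome without naming it. If that outcome is graft failure, the model is valid, but the three numeric endpoints have no adjusted analysis. If it means the whole list, the model does not fit three of the four.

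These three endpoints are the quantitative output of two invasive modalities, IVUS and NIRS. They address part of the purpose in Section 5, namely whether wall thickening and lipid deposition are reduced. The main risk is discretion: a test or cut-point chosen after seeing the results can push the false-positive rate above 5%. Loss of power is a second risk, and arises only if the analyst dichotomises in order to follow the text.

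**Working it through.** **Match of test to data**

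| Endpoint | Type (Section 11) | Cut-off | Test (Section 13) | Can it be run? |
|---|---|---|---|---|
| Angiographic graft failure | binary | ≥75% stenosis | Fisher | yes |
| Total atheroma volume | numeric | none | Fisher | no |
| Normalized total atheroma volume | numeric | none | Fisher | no |
| Lipid core burden index | numeric | none | Fisher | no |

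This establishes the defect. The rest only illustrates what the open choice could do.

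**The sample size used.** Section 13 derives 48 evaluable per arm for OCT thrombus (25% vs 5%, 80% power, two-sided 0.05). With the pooled normal approximation:

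n = [1.960·√(2·0.15·0.85) + 0.842·√(0.25·0.75 + 0.05·0.95)]² / 0.20² = (0.990 + 0.408)² / 0.04 ≈ 48.8, so 49 against the stated 48.

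48/(1 − 0.20) = 60, as stated. Power at control rates of 20, 25 and 30% comes to 68.0, 79.3 and 87.7%, against the stated 67, 80 and 89%. The figures reproduce closely, but they concern the binary primary endpoint. I borrow 48 per arm for the illustration.

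**False-positive rate, no true effect, 48 per arm.** Cutting at the pooled median leaves 48 patients above and 48 below. Fisher's test rejects at a split of 30 vs 18 (p = 0.024) but not at 29 vs 19 (p = 0.066), so its exact size is 2.4%. Taking the smallest p-value over several cuts (60,000 simulated null trials; the last row 10,000):

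| Choice left to the analyst | Rejection rate |
|---|---|
| Best of 3 quartile cuts | 7.6% |
| Best of 5 cuts (quartiles and tertiles) | 8.7% |
| Best of 9 decile cuts | 13.4% |
| Best of 3 quartile cuts or a t-test | 9.4% |

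**Power, 48 per arm, normal data, assumed standardized difference d.** The t-test column uses the noncentral t distribution with 94 degrees of freedom and noncentrality d·√(48/2). The Fisher column is simulated with a cut at the pooled median.

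| d | t-test | Median split + Fisher |
|---|---|---|
| 0.195 | 16% | 7% |
| 0.3 | 31% | 14% |
| 0.5 | 68% | 38% |
| 0.58 | 80% | 50% |
| 0.8 | 97% | 80% |

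The first row uses the only related figure in the documents, the endpoint "SVG intimal area at follow-up IVUS" of the 113-patient clopidogrel trial in Section 6, Table 1: d = (4.5 − 4.1)/√[(2.1² + 2.0²)/2] = 0.4/2.051 = 0.195. That is a different measure, so it is an anchor only. The value 0.58 is by construction the effect at which a t-test has 80% power with 48 per arm.

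With skewed data (lognormal, log-scale SD 0.8, d = 0.5 on the log scale), power is 66% for Wilcoxon, 56% for a t-test on raw values, and 38% for the median split with Fisher.

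**Sensitivity to n.** Fisher's test is discrete, so its figures jump with sample size. Simulated with 20,000 trials per n:

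| n per arm | Exact size, median cut | Fisher power, d = 0.5 | t-test power, d = 0.5 | Best of 3 cuts, null |
|---|---|---|---|---|
| 40 | 4.4% | 41% | 60% | 7.2% |
| 42 | 4.9% | 44% | 62% | 11.2% |
| 44 | 1.9% | 32% | 64% | 6.0% |
| 48 | 2.4% | 38% | 68% | 7.5% |
| 60 | 4.4% | 56% | 78% | 7.2% |

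The power gap and the rejection rate above 5% are present at every n in the table.

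**The case against.** The strongest reply is that this is a drafting slip. The logistic sentence is in the singular, and its covariates are those the primary analysis describes as influencing graft failure. Fisher and logistic regression were probably written for graft failure, and the numeric measures were swept into the same sentence. A competent statistician would use a t-test or a rank test, and nothing in the text suggests a search over cut-points. That is plausible, and it makes the cut-point figures an upper-end scenario. But the sentence is the only instruction given for these endpoints, and departing from it still leaves a choice. The skewed example shows that t-test versus Wilcoxon is not neutral for power. I have not computed the false-positive rate from choosing between those two alone, and would expect it to be smaller than the cut-point figures.

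Second, this is an abbreviated protocol that refers to an attached sponsor's protocol, which was not supplied and may name another test. That stands as a limit on the finding. If that document does name another test, the two texts conflict and this sentence still needs correcting.

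Third, 48 per arm gives a small Fisher size, so 38% against 68% is a wider gap than some nearby sample sizes give (44% against 62% at 42 per arm). This is correct; the gap narrows there but does not close.

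Finally, leaving secondary endpoints unadjusted for multiplicity is openly declared and is a separate choice. I agree. It matters here only because no correction would absorb a rate raised by discretion.

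**Conclusion.** The concern holds for the supplied text. Three of the four endpoints assigned to Fisher's exact test are numeric with no cut-off, and no alternative is named. As written, the IVUS and NIRS endpoints have no executable prespecified comparison. This is a wrong specification rather than missing detail.

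The practical size is uncertain, because the documents give no SD, effect size or evaluable number for these measures. Assuming 48 per arm, free choice among three to nine cuts gives about 7.6% to 13.4% false positives. Cutting at the median, with normal data and an assumed 0.5 SD difference, costs about 30 percentage points of power (68 − 38). The precise values depend on n, the distribution and the cuts.

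Only secondary endpoints are involved. The primary efficacy, severe bleeding and MACE analyses stand. The correction should be made, but it does not threaten the trial's main conclusion.

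**What to change.** Split the sentence in Section 13.

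- **Graft failure:** keep Fisher's exact test and the logistic model, and name angiographic SVG failure as the outcome of that model.
- **Total atheroma volume, normalized total atheroma volume, lipid core burden index:** name one unadjusted comparison for each, either a t-test or, if skew is expected, a Wilcoxon rank-sum test. Make the choice in the text now rather than leaving it conditional on the data.
- **Adjusted analysis of the three:** a linear model, on a stated transformed scale if skew is expected, using the covariates already listed that are measured before randomization. Table 2 schedules graft imaging only at 12 months, so state where minimum graft diameter comes from. Including the randomization strata is optional. The pump stratum will add little, since "nearly all coronary bypass graft surgeries are performed on-pump at our institution" (Section 6).
- **Reporting:** the between-group difference with 95% confidence interval, and the number evaluable for each modality. Those numbers may differ, because in Section 12 the NIRS catheter is "positioned to the same location where the IVUS catheter was previously placed, if feasible".
- **Cut-offs:** if any measure is to be analysed as a category, state the threshold now.

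Naming the numeric-data test is the essential part; the adjusted model and the reporting items complete it. The cost is one paragraph of analysis wording, with no change to sample size, data collection or conduct. It must be settled before unblinding, and checked against the attached sponsor's protocol so that the two agree.

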Lipid lowering therapy can significantly reduce atherosclerosis risk in a variety of high and low-risk populations. Four trials have specifically examined the role of lipid-lowering therapy in SVGs: (1) the Post-Coronary Artery Bypass Graft (POST-CABG)^{23, 24} trial evaluated lovastatin and if needed, cholestyramine; (2) the Lopid Coronary Angiography Trial (LOCAT)²⁵ evaluated gemfibrozil; (3) the Cholesterol Lowering Atherosclerotic Study (CLAS)²⁶ evaluated colestipol and niacin; and (4) the study by Makuuchi et al evaluated pravastatin vs placebo.²⁷ The first 3 trials showed reduction in the

angiographic progression of SVG disease. The POST-CABG and the CLAS trials also demonstrated a reduction in clinical events.

Although administration of aspirin and statins is the current standard of care for preventing early SVG failure, 29-46% of patients experience SVG failure during the first year post CABG.^{4, 5} Therefore, additional therapies are needed to further decrease the SVG failure risk of those patients.

Investigative therapies for early SVG failure prevention

Several therapies are currently being evaluated to prevent early SVG failure. Those therapies address different stages of the SVG disease process, starting at the time of CABG surgery and continuing through the initial year post implantation.

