For safety monitoring, any emergency adverse event resulting from participation in the study will be treated at the Dallas VA Medical Center. [name] will evaluate all adverse events and determine the appropriate course of action.

If a patient develops severe bleeding during the study period, prasugrel will be temporarily held and will be discontinued if the patient is considered to be at increased risk for recurrent bleeding. If a patient develops an indication for receiving oral anticoagulation therapy with warfarin or dabigatran during his or her participation in the study, prasugrel administration will be discontinued to minimize the risk of bleeding.

If any subjects are hospitalized for an acute coronary syndrome or undergo coronary angiography at an outside hospital, the hospitalization records will be obtained and reviewed by the clinical events committee. The Universal definition of myocardial infarction will be used for diagnosing myocardial infarction. Bleeding will be assessed with the use of the GUSTO criteria.⁶⁷ Severe bleeding will be defined as fatal bleeding, intracranial hemorrhage, or bleeding causing hemodynamic compromise requiring blood or fluid replacement, inotropes, or surgery.⁶⁷ The frequencies of moderate bleeding, defined as bleeding requiring transfusion not characterized as severe, and moderate/severe and severe bleeding will also be analyzed. Information on (surgical or percutaneous) coronary revascularization will also be collected. Data will be entered on paper-based case report forms and will be double-entered into a secure, password protected database, accessible only by study personnel. Subjects will be identified by a unique study number in the database.

Additionally a Data Safety Monitoring Board will be appointed to review the study periodically (every 12 months, or sooner if required).

15. RISK/ BENEFIT ASSESSMENT:

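### MACE counts any coronary revascularization, so procedures prompted only by the 12-month research angiogram can enter a clinical endpoint, depending on whether and when a patient is scanned

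*Combined protocol and SAP*

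**What the plan says.** All references are to the combined protocol and SAP.

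- **Definition.** Section 13 (Statistical Analysis of secondary endpoints) defines MACE as a "composite of death, acute coronary syndrome, and coronary revascularization". The revascularization component has no qualifier.
- **Period.** Section 11 lists as a secondary endpoint "the incidence of major adverse cardiac events and moderate bleeding during the 12-month study period". Section 13 says the incidence "at 12 months will be compared between the two study groups using the chi-square test", and that Kaplan-Meier curves and the "log-rank test will be used to compare time-to-event of major adverse cardiac events in the two study groups". It gives no censoring rule and no cut-off relative to the study catheterization.
- **Research angiogram.** Section 12 states: "Examination of the target SVG lesion with angiography, OCT, IVUS, and NIRS will be obtained at 12 months post CABG". Table 2 gives this visit a window of 30 days either side and adds a phone call, the "Post-Treatment Follow-up Contact (30 days after 12 month visit".
- **Early clinical angiograms.** Under rule (a) in section 12, a clinically indicated graft angiogram at 10 months or more after enrollment also serves as the study imaging.
- **Data collected.** Section 14 says: "Information on (surgical or percutaneous) coronary revascularization will also be collected". It does not mention indication or trigger. The clinical events committee is described only as reviewing records of hospitalization for acute coronary syndrome or of angiography at an outside hospital.
- **Background rate.** Section 6 states that "29-46% of patients experience SVG failure during the first year post CABG".

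**The concern.** Section 5 asks whether prasugrel leads to fewer clinical events, and MACE is the efficacy endpoint that addresses this. Under the stated definition, a silent stenosis that is found only because the protocol required an angiogram, and is then treated, is a MACE event if it falls within the counting period. Three problems follow.

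1. **Event status depends on the scan.** After an angiogram at month 11, the procedure can fall inside 12 months. After one at month 13, the same finding may fall outside. A patient who is never imaged cannot contribute such an event, and the plan allows for 20% dropout.
2. **The endpoint overlaps with another.** Angiographic SVG failure (at least 75% diameter stenosis in at least one graft) is already a secondary endpoint. Procedures prompted by that finding carry it into MACE under a clinical label.
3. **The curves are affected late.** Triggered procedures would cluster at the end of the Kaplan-Meier curves, around the scan.

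The likely scale is uncertain but not obviously trivial. The Figure 1 legend in section 6 says that the excess risk after early graft failure in the cited earlier trial came mainly from repeat revascularization, which is the unqualified component here.

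**Working it through.** **The plan's own figures.** The plan gives no rate, effect or power for MACE. Its only calculation is for the OCT endpoint: 25% vs 5%, 80% power, two-sided 0.05. The pooled normal approximation gives 49 per group against the stated 48. Allowing for 20% dropout, 48/0.80 = 60, as stated. With 48 per group and an 80% relative reduction, power at control rates of 20%, 25% and 30% is 68%, 79% and 88%, against the stated 67%, 80% and 89%. These figures reproduce adequately and are untouched by this point. The same approximation is used below.

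**Model for MACE.** Let p be the clinical MACE risk, and q the share of clinically event-free patients who have a procedure only because of the research angiogram, inside the counting period. Then

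observed risk P = p + (1 - p) × q.

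Power with n = 60 per arm is Φ[(d - 1.96 × SE0)/SE1], where d is the difference in P, SE0 = √(2 × P̄(1 - P̄)/n) with P̄ the mean of the two risks, and SE1 = √([P1(1 - P1) + P2(1 - P2)]/n).

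**Inputs.** The 60 per arm comes from section 13. Both p and q are assumptions, because the document gives neither. For illustration, p = 16% on placebo and 8% on prasugrel.

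Worked baseline (q = 0): SE0 = √(2 × 0.12 × 0.88/60) = 0.0593 and SE1 = √((0.1344 + 0.0736)/60) = 0.0589. Then (0.08 - 0.1163)/0.0589 = -0.616, so power is 27%.

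| q placebo / prasugrel | P placebo | P prasugrel | Risk ratio | Power |
|---|---|---|---|---|
| 0 / 0 | 0.160 | 0.080 | 0.50 | 27% |
| 5% / 5% | 0.16 + 0.84 × 0.05 = 0.202 | 0.08 + 0.92 × 0.05 = 0.126 | 0.62 | 20% |
| 10% / 10% | 0.16 + 0.84 × 0.10 = 0.244 | 0.08 + 0.92 × 0.10 = 0.172 | 0.70 | 16% |
| 10% / 5% | 0.244 | 0.126 | 0.52 | 38% |

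With 10% triggered in both arms, such procedures make up 0.084/0.244 = 34% of placebo events and 0.092/0.172 = 53% of prasugrel events.

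**No clinical effect.** Take p = 15% in both arms and q = 15% vs 5%. Then P = 0.15 + 0.85 × 0.15 = 0.2775 and 0.15 + 0.85 × 0.05 = 0.1925, a risk ratio of 0.69. A purely angiographic difference would appear as a clinical one.

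**The case against.** **Size.** A reader might multiply out the section 6 rate: 96 evaluable patients × 29-46% gives 28-44 failed grafts, and if 20-50% were treated, 6-22 triggered events. The document does not support this as an estimate. The treatment share is an assumption, and section 7 describes treatment options for severe or occluded grafts as limited. The 29-46% is all first-year failure, including failures that have already presented clinically. The product also assumes that every scan falls before the cut-off. It is an upper range at best.

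**Direction.** A reader might infer that the effect must be pulled towards the null. That needs equal triggered rates. If prasugrel reduces graft stenosis, triggered rates would be lower on prasugrel, and the 10% vs 5% row shows power rising. The added power would, however, come partly from an angiographic effect, so this does not rescue the clinical reading.

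**Relevance.** MACE is an unpowered secondary endpoint, and the 16% vs 8% is not from the document. The nearest figure there is the CABG subgroup of the clopidogrel trial in acute coronary syndrome: 14.5% vs 16.2%, with a different composite. At those rates power with 60 per arm is about 4%, with or without equal triggered rates of 5-10%. This stands: little power is at stake. The interpretation of the estimate still is.

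**Bias.** A reader might suspect that treatment decisions favour one arm. Patients, coordinators and image analysts are blinded, which limits differential judgement. It prevents neither dilution nor overlap.

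**Completeness.** This is an abbreviated protocol that refers to an attached sponsor's protocol, which is not available here. A qualifying definition or committee rule could sit there. The available text has none.

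**Conclusion.** The point holds. Applied as written, the MACE definition admits procedures prompted only by the research angiogram, and makes event status depend partly on whether and when a patient is scanned. This follows from the stated definition and visit schedule and does not depend on the illustrative numbers.

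Neither size nor direction can be derived from the document. On the assumed 16% vs 8%, equal triggered rates of 5-10% weaken the risk ratio from 0.50 to 0.62-0.70, while 10% vs 5% leaves it near 0.52 with higher apparent power.

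The primary OCT comparison and the severe-bleeding analysis are not affected. The change is worth making before data are analysed, but the trial's main conclusion does not turn on it.

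**What to change.** 1. **Definition.** For the MACE analyses, count only clinically driven revascularization, meaning symptoms, acute coronary syndrome or documented ischaemia.
2. **Recording.** Enter the indication and its date on the case report form before the research angiogram, and classify them blind to treatment arm. Where a clinically indicated angiogram at 10 months or more doubles as study imaging under section 12 rule (a), classify by its clinical indication.
3. **Cut-off.** Follow death, acute coronary syndrome and clinically driven revascularization to one fixed 12-month cut-off in all patients, scanned or not, for both the chi-square and log-rank analyses.
4. **No censoring at the study catheterization.** Censoring may look like the simpler remedy. Under rule (a), however, it would drop genuine later deaths, coronary syndromes and symptom-driven procedures, and it would leave unequal follow-up for the 12-month chi-square test.
5. **Supportive count.** Report any revascularization, including study-triggered procedures, by arm.

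**Cost.** A few sentences in section 13 and a case report form field for indication and date. The existing phone contact 30 days after the 12-month visit reaches month 12 even for a visit at the earliest edge of the window (12 months - 30 days + 30 days). Patients imaged earlier under rule (a) need confirmed follow-up to the same cut-off. The downside is somewhat fewer MACE events. This is a counting rule only and changes no patient's care.
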